2. HYPOTHESIS AND OBJECTIVES

1. Hypothesis

Specific Aim 1. In a randomized sham-control trial (n=60), determine the efficacy of home TTNS in SCI.

Hypothesis 1.1: Those in the TTNS group will be able to reduce their OAB medication dosages while maintaining continence compared to controls over a period of 3 months.

Hypothesis 1.2: Symptoms of NGB measured by the Neurogenic Bladder Symptom Score (NBSS) and a voiding diary (VD) will be reduced in the TTNS group compared to controls.

Specific Aim 2. Determine the impact on quality of life using TTNS at home.

Hypothesis 2.1: Incontinence-related QOL (I-QOL) will be increased in the TTNS group compared to the controls and from baseline.

Hypothesis 2.2: Anticholinergic side effects will be decreased in the TTNS group at 3-months compared to the controls and from baseline.

2. Primary Objectives

OBJECTIVE: to advance the science and care around bladder function and management among people with spinal cord injury/disease (SCI/D) and NLUTD with TTNS (and if so, we anticipate translating this research to other populations with NLUTD). Specifically, we seek to demonstrate that TTNS will improve NLUTD in SCI/D by:

1. intervening acutely with neuromodulation of the neurogenic bladder via TTNS to maintain bladder capacity by reducing pathologic reflexes, DH and DSD;
2. altering pathologic autonomic nervous system (ANS) responses and reducing autonomic dysreflexia (AD).
3. improving the quality of life (QOL) of those living with SCI/D by providing a feasible, non-pharmacologic, and dignified intervention for NLUTD that can be performed at home;

In this proposed study, we seek to provide evidence for overall objective #3 using home TTNS. We hypothesize that TTNS can be used in the home setting to maintain continence while reducing OAB medication dosages and improve quality of life.

Primary Objective 1: Evidence of TTNS efficacy with reduced OAB medication dosage

Primary Objective 2: Evidence of TTNS efficacy with reduced NGB symptoms as measured by the NBSS and the Voiding Diary

3. Secondary Objectives

Secondary Objective 1: I-QOL scores will be increased in the TTNS group compared to the controls

Secondary Objective 2: Anticholinergic side effects will be reduced in the TTNS group compared to the controls.

4. Potential Risks and Benefits:

a. End Points - Efficacy

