Primary Objective 1: Evidence of TTNS efficacy with a greater proportion of bladder medication reduction in the TTNS group compared to the control group. Time to achieve this endpoint will be approximately 3 months after subject recruitment, anticipated 1 year to complete all subject recruitment.

Primary Objective 2: Evidence of TTNS efficacy with reduced NGB symptoms as measured by the NBSS and the Voiding Diary. Time to achieve this endpoint will be approximately 3 months after subject recruitment, anticipated 1 year to complete all subject recruitment.

b. End Points- Quality of Life

Secondary Objective 1: Improved QOL in the TTNS group compared to the controls at the end of the 3-month trial, based on I-QOL scores. Time to achieve this endpoint will be approximately 3 months after subject recruitment, anticipated 1 year to complete all subject recruitment.

Secondary Objective 2: Decreased anticholinergic side effects in the TTNS group compared to the controls at the end of the 3-month trial, based on an anticholinergic side effect survey. Time to achieve this endpoint will be approximately 3 months after subject recruitment, anticipated 1 year to complete all subject recruitment.

c. End Points - Safety

Urinary Tract Infection (UTI) risk:

We expect the rates of morbidity to be the same between those who participate and those who do not. However, because UTI is directly related to the bladder, we will focus on the occurrence of UTI. Based on literature, the overall rate of UTI in SCI is about 2.5 episodes per patient per year. As a result, we expect to see 0.6 episodes per patient during the 3-month study period. Based on that, we construct the stopping rules to stop at 20% UTI rate using lower 90% exact Blyth-Still-Casella confidence bounds. If the number of patients with UTI exceed 3 in the first 5 patients, 4 in the first 10 patients, or 5 in the 14 patients, then patient accrual will be paused pending a review by a medical advisory board comprised of SCI experts.

Bladder medication discontinuation risk:

- Worsened incontinence

Electric Stimulation Risks:

Electric stimulation is commonly performed on the extremities of those with spinal cord injury at the study institution. There are few adverse reactions to electric stimulation. The common ones include:

- Pain with electric stimulation: in these cases, the intensity is reduced until it is comfortable.

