Medication reduction protocol: Subjects will be using up to 2 anticholinergic OAB medications. Subjects generally use similar medications with a common approach- maximize one medication before adding a second medication. The PI will provide a weekly weaning schedule, individualized for each subject. No changes will occur during the first 2 weeks of TTNS. Starting week 3, the secondary OAB medication will be halved if possible, otherwise discontinued. Should the subject tolerate this, weaning will continue until one medication is discontinued, then the other. If the subject does not tolerate weaning, they will remain on the lowest, tolerable dose and we will attempt weaning the following week.

- Information gathered:
 - Clinical demographics, morbidity, and Neurologic Exam findings from interview with subjects, exam, and EMR review.
 - Bladder diary will include:
 - use of TTNS with amperage and presence of toe flexion, and pain score 0-10
 - log of catheterization, volumes
 - log of incontinence episodes
 - Description of other observed changes, including but not limited to: fatigue, vision changes, mental status, bowel program changes, and sexual function changes.
 - I-QOL at baseline initial visit and then at 3-month follow-up. Can be conducted over phone.

- NBSS at baseline and every 4 weeks (monthly) and at the 3-month follow-up. Can be conducted over phone.
- Anticholinergic survey at baseline and then at 3-month follow-up. Can be conducted over phone.
- TTNS satisfaction survey at 3-month follow-up. Can be conducted over the phone.
- Information will be tabulated on an Excel spreadsheet on my personal work desktop, password protected. Any paper data (bladder diary) will be de-identified and retained in a locked drawer in the locked office of the PI.
- General self-efficacy at baseline, week 6 and at the end of the trial. Can be conducted over the phone.
- CD-RISC at baseline, week 6 and at the end of the trial. Can be conducted over the phone.
- The medication and TTNS adherence survey at baseline then every 4 weeks. Can be conducted over the phone.
- The medication and TTNS % survey at baseline then every 4 weeks. Can be conducted over the phone.

1. Summary of Study Design

A randomized control trial of TTNS v sham-control in chronic SCI (n=60) performing intermittent catheterization on OAB medications will be performed to address the following Specific Aims:

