Patients will be randomized to control and TTNS at a 1:1 ratio by computer-generated sequences, with stratified allocation in blocks of 4 controlling for complete SCI, with the investigator blinded to the treatment allocation. Changes in outcomes listed in Aim 1 and 2 will be compared between groups by two-sample two-sided t-test or Wilcoxon rank-sum test. Descriptive statistics and mean plots will be provided for the longitudinal measurements. Multilevel mixed-effects regression models will be used for longitudinal analyses of treatment effects, controlling for confounding variables including age, sex, severity of SCI, compliance (number of sessions), and OAB medication dosages. Multiple testing will be adjusted by Bonferroni correction if necessary. Non-random missing data will be analyzed using the method in Ibrahim and Molenberghs.²³ Considering the unknown long-term effects of TTNS, we may not see significant treatment effect on some outcomes by conventional (frequentist) analyses. We plan a Bayesian analysis (with either skeptical or neutral priors) to estimate the probability (with 95% credible intervals) of treatment effect. Conventional analysis will be performed in SAS 9.4 (SAS Institute, Cary NC) and Bayesian analysis will be performed in R 3.5.0 using packages like R2WinBUGS.

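### NBSS (Primary Objective 2) has two planned tests of the treatment effect and no named deciding one, so its false-positive rate is roughly 7–9% instead of 5% if either may carry the claim.

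*Combined protocol and SAP*

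**What the plan says.** Section 2 makes NBSS part of a primary objective: "Primary Objective 2: Evidence of TTNS efficacy with reduced NGB symptoms as measured by the NBSS and the Voiding Diary". The efficacy endpoints in section 2.4.a place it at the end of follow-up: "Time to achieve this endpoint will be approximately 3 months after subject recruitment". Section 5 gives repeated measurement, "NBSS at baseline and every 4 weeks (monthly) and at the 3-month follow-up", and the schedule of events agrees (baseline and weeks 4, 8 and 12). Section 1.2.d instead lists NBSS at baseline and 3 months only.

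Section 11.2 gives the first analysis: "Changes in outcomes listed in Aim 1 and 2 will be compared between groups by two-sample two-sided t-test or Wilcoxon rank-sum test". The mixed model follows: "Multilevel mixed-effects regression models will be used for longitudinal analyses of treatment effects", controlling for confounders that include "age, sex, severity of SCI, compliance (number of sessions), and OAB medication dosages". On multiplicity it says only: "Multiple testing will be adjusted by Bonferroni correction if necessary". A Bayesian analysis is added without a fixed prior: "We plan a Bayesian analysis (with either skeptical or neutral priors) to estimate the probability (with 95% credible intervals) of treatment effect".

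No section calls any of these primary, supportive or sensitivity. The time coding and contrast of the model are not given, nor is a rule for choosing between the t-test and the Wilcoxon test. The sample-size text for Aim 1.2 names no test.

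**The concern.** A single endpoint has two frequentist routes to a positive result. They need not estimate the same quantity. A test on change to 3 months looks at week 12. A model average over visits gives equal weight to week 4, although section 5 starts weaning only in week 3. A trend test asks a third question.

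If the choice is made after the data are seen, the NBSS part of Primary Objective 2 can be declared met on whichever analysis crosses 0.05, and the error rate for that endpoint exceeds the nominal level. If the two conflict, the plan gives no rule for which one stands. This problem sits within one endpoint and would remain even if NBSS were the only endpoint in the trial.

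**Working it through.** **Inputs**
- NBSS at weeks 0, 4, 8 and 12 (section 5 and its schedule of events).
- Two-sided 0.05: stated in section 11.1 for Aims 1.1 and 2.1, assumed here for NBSS.
- Completers per arm: 30 × (1 − 0.40) = 18 from the dropout in section 11.1, or (60 − 6)/2 = 27 from section 5.
- Visit correlation: not given. Assumed exchangeable 0.3–0.7, or first-order autoregressive 0.6–0.8.
- Complete, normally distributed data. The listed covariates are not modelled.

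**The plan's own figure.** Section 11.1 gives 20 for NBSS from a mean difference of 11.8 (11), without unit, power or test. Reading 11 as the SD, n per group = 2(z₀.₉₇₅ + z_power)²(SD/Δ)².
- 80% power: 2 × (1.960 + 0.842)² × (11/11.8)² = 13.6, so 14 (15 by t-test).
- 90% power: 2 × (1.960 + 1.282)² × 0.869 = 18.3, so 19 (20 by t-test).

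So 20 fits only as 20 per group at 90% power, which is not stated. The calculation does not show which analysis decides. The documents give no error rate for the set of NBSS analyses.

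**Step 1: no true effect.** Let D be change to week 12 (the two-group test) and M the model contrast, each tested at 0.05. Then P(either) = 0.05 + 0.05 − P(both), where P(both) comes from a bivariate normal with correlation r between the two estimates. For exchangeable correlation ρ:

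| Model contrast | r | r at ρ = 0.3 / 0.5 / 0.7 | P(either) |
|---|---|---|---|
| Average over visits, no baseline term | [(1−ρ)/3] / √[2(1−ρ)(1+2ρ)/3] | 0.27 / 0.20 / 0.14 | 9.6 / 9.6 / 9.7% |
| Average, baseline as covariate | √[(1+3ρ)/6] | 0.56 / 0.65 / 0.72 | 8.9 / 8.6 / 8.3% |
| Average change from baseline | √(2/3) | 0.82 throughout | 7.7% |
| Week 12, baseline as covariate | √[(1+ρ)/2] | 0.81 / 0.87 / 0.92 | 7.8 / 7.3 / 6.8% |

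Example, second row at ρ = 0.5: r = √(2.5/6) = 0.645, P(both) = 0.0142, P(either) = 0.100 − 0.0142 = 8.6%. The ceiling for two independent tests is 1 − 0.95² = 9.75%. Autoregressive correlation gives 9.6–9.7%, 8.0–8.7%, 7.0–7.2% and 7.3–7.9% for the four rows. Simulated t-tests (20,000 null trials per setting, 18 and 27 per arm) agree with these values to within about half a percentage point, so the two dropout figures make no practical difference here.

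**Step 2: a true effect.** These runs use 27 per arm and exchangeable ρ of 0.3–0.7. The effect builds over weeks 4, 8 and 12 as 0.2/0.5/0.75 SD or 0.1/0.4/0.75 SD. The change test and the model average fall on opposite sides of 0.05 in:
- about 11–30% of trials with baseline as covariate;
- about 17–34% with average change from baseline;
- about 37–58% with no baseline term.

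With 18 per arm and baseline as covariate, the same set-up gives about 22–32%. At the plan's own effect, 11.8/11 = 1.07 SD, with 27 per arm and baseline as covariate, the rate is about 1–13% for building effects on the same pattern and at most about 10% for a constant effect.

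**Step 3: what the model conditions on.** The number of sessions accrues after randomisation. OAB dosage changes from week 3 and is the outcome of Primary Objective 1. Unless baseline dosage is meant, the model adjusts for variables that treatment can affect, so the two analyses may estimate different effects even at the same visit. The figures above do not include this.

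**The case against.** The best defence is that a hierarchy can be read from the text. The endpoint is set at about 3 months, the test on change comes first and covers all Aim 1 and Aim 2 outcomes, and Aim 2.1 is sized on a t-test. The Bonferroni sentence speaks of multiple testing in general and is not limited to endpoints. Some disagreement also arises between any primary analysis and its supportive analyses.

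Part of this stands. The 3-month timing does favour a week-12 comparison, and disagreement is harmless once one analysis is named. But order of listing is not designation, and the model is described as estimating treatment effects, not as a sensitivity analysis. The Bonferroni clause is conditional and defines no family. It could lower the threshold, but it cannot say which of two conflicting results for one endpoint stands.

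The schedule in section 1.2.d could also be cited, since with NBSS at baseline and 3 months only there would be little longitudinal to model. Section 5 and its schedule of events contradict that, and the deciding analysis would still be unnamed.

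**Conclusion.** The point holds at moderate size. If either analysis may carry the claim at 0.05, the false-positive rate for NBSS is roughly 7–9% with baseline in the model and up to about 10% without. Disagreement is about 11–30% for an assumed effect building to 0.75 SD (baseline as covariate, 27 per arm), and less at the plan's 11.8 (11) if 11 is the SD. All of this rests on assumed correlations, complete data and 0.05 applied to NBSS. It also reads NBSS as a superiority endpoint, as in Hypothesis 1.2; section 5.1 also describes it as a check that symptoms stay stable.

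A reader might infer more than the documents support:
- **An error rate of 10–12%, or disagreement in 37–58% of trials.** The higher error rates need Wilcoxon or trend tests counted as extra chances, and the disagreement range needs a model with no baseline term. The plan offers the t-test and Wilcoxon as alternatives, mentions no trend test, and gives its covariates as an open list that does not rule out baseline.
- **The Bayesian analysis as another test at 0.05.** It yields a posterior probability, not a p-value.
- **An intention to pick the favourable result.** Nothing says so; the plan simply leaves the choice open.

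The trial is not invalidated, but a primary-objective claim has no fixed decision rule.

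**What to change.** Before unblinding, state in section 11.2:

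> The deciding analysis for NBSS is the TTNS-minus-sham difference at week 12, two-sided 0.05, from a mixed model with categorical visit, treatment-by-visit, baseline NBSS and the randomisation stratum (complete/incomplete SCI). Compliance and on-study OAB dosage are not covariates in this model. The two-group test on change, the average over visits, any time-trend test and models adjusting for compliance or OAB dosage are supportive and cannot by themselves establish efficacy.

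The covariate sentence is essential. Making the mixed model decisive as it now stands would put an estimate that appears to be conditioned on post-randomisation variables above the randomised comparison. Naming the week-12 test on change instead would also remove the ambiguity; what matters is choosing one.

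Also reconcile section 1.2.d (NBSS at baseline and 3 months only) with section 5 and its schedule of events (every 4 weeks).

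The cost is a few sentences and no new data. The downside is that a positive supportive analysis can no longer carry the claim. If the sponsor wants one two-group test and one model contrast both to count, each should be tested at 0.05/2 = 0.025. For 11.8 with SD 11, approximate power for the two-group test is then 97% with 30 per arm and 84% with 18.

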3. STUDY POPULATION

1. List the number of subjects to be enrolled.

60 subjects. Consecutive SCI clinic encounters meeting the inclusion/exclusion criteria will be asked to enroll. Children and pregnant women will be excluded.

2. Criteria for Recruitment

- Initial screening will be performed in the clinic with the subject and PI
- In those interested, they will be given an IRB-approved consent form to review and to sign.
- Those with tetraplegia will unlikely have the ability to sign and we will have a 3rd party attest to the consent.
- Patients will ideally decide to participate in clinic, but can always decide at a later date and return to clinic to trial the TTNS as part of the I/E criteria.
- Flyers will be posted and distributed in the outpatient clinic to increase study awareness.

3. Inclusion Criteria (table 1)

Inclusion criteria: 1) ages 18-75 years; 2) SCI performing IC; 3) up to 2 anticholinergic OAB medications; 4) stable OAB medications in the past 2 months; 5) SCI neurologic level above T10; 6) English and Spanish speaking. Subjects that satisfy initial screening and willing to participate in the trial will have electric stimulation placed to attempt toe flexion as a check of the tibial nerve integrity. Those who cannot achieve toe flexion will be excluded.

Table 2. Inclusion and Exclusion Criteria

Inclusion Criteria	Exclusion Criteria
18-75 years old Traumatic and Non-traumatic SCI performing IC	Past history of genitourinary diagnoses or surgeries History of CNS disorders and/or peripheral neuropathy
Up to 2 anticholinergic OAB medications	Pregnancy
No changes in OAB medications	Lower motor neuron bladder
Neurologic level of injury above T10	Concern for tibial nerve pathway injury
English and Spanish speaking	Absence of toe flexion or AD with electric stimulation Bladder chemodenervation in past 6 months Potential for progressive SCI including neurodegenerative SCI, ALS, cancer myelopathy, Multiple sclerosis, transverse myelitis

SCI= spinal cord injury; IC= intermittent catheterization; OAB= overactive bladder; T10= thoracic level 10; CNS= central nervous system; AD= autonomic dysreflexia

4. Exclusion Criteria (table 1)

Subjects meeting any of the exclusion criteria at baseline will be excluded from participation:

- History of genitourinary diagnoses (i.e. prostate hypertrophy, overactive bladder, cancer, etc.)

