Subjects will have their first study visit after their normal clinic visit. Once consented, we will trial TTNS for a response of toe flexion. If they have a response, they will be included in the study. If no response or not tolerating electric stimulation, they will not be included in the study.

Participants will have direction in clinic on the use of the Stamobil+, including written, oral, and smartphone images/video if they have access.

The electric stimulation protocol will use stimulation frequency of 10 Hz and pulse width of 200ms in continuous mode for 30 minutes daily, beginning as soon as possible. The goal is 5 days per week of TTNS use for 3-months.

Subjects will be called weekly to capture the information of the TTNS log and to monitor progress of protocol. They will also be reminded to change electrodes weekly. 3 days prior to the NBSS call, the RA will contact the subjects to remind them to begin recording in their voiding diary for 2 days.

- *Final Study Visit:*

Upon completion of the 3-month study period, final voiding diary information will be collected and the post-trial questionnaires will be conducted.

- *Post Study Follow up and Procedures*

The data will be statistically analysed in the post-study follow up. Subject participation is not required.

- *Discontinuation Visit and Procedures*

If withdrawal occurs, no evaluation will be required for the final study visit, regardless of the withdrawal reason. There are no safety risks in withdrawing from this study at any point. OAB medications can be resumed at the prior efficacious dose.

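### The mixed models for the treatment effect adjust for sessions completed and for an undated OAB dose, so their arm coefficient need not be the randomised effect

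*Combined protocol and SAP*

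**What the plan says.** Section 11.2 plans two kinds of between-group analysis. Changes in the Aim 1 and Aim 2 outcomes "will be compared between groups by two-sample two-sided t-test or Wilcoxon rank-sum test". In addition, "Multilevel mixed-effects regression models will be used for longitudinal analyses of treatment effects". The adjustment in these models is described as "controlling for confounding variables including age, sex, severity of SCI, compliance (number of sessions), and OAB medication dosages". No covariate is given a measurement time. The adjusted model is not labelled per-protocol, mediation or sensitivity, and neither analysis is named as primary.

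Other sections bear on two of the covariates:

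- **Sessions.** Section 6 (Study Visits and Procedures) says "The goal is 5 days per week of TTNS use for 3-months". Section 5 gives both arms the same instruction on use.
- **OAB dose at entry.** Section 3 (Inclusion Criteria) requires "stable OAB medications in the past 2 months", so a baseline dose is well defined.
- **OAB dose on study.** Section 2 states "Primary Objective 1: Evidence of TTNS efficacy with reduced OAB medication dosage". Under the medication reduction protocol in Section 5, dose changes from week 3 according to tolerance: "If the subject does not tolerate weaning, they will remain on the lowest, tolerable dose and we will attempt weaning the following week". Section 3 (Withdrawal Criteria) has medication use logged monthly.
- **Repeated outcome.** Section 5 schedules "NBSS at baseline and every 4 weeks (monthly) and at the 3-month follow-up", which makes NBSS a natural outcome for the longitudinal model.

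**The concern.** A confounder of a treatment comparison is a cause of both treatment and outcome. Assignment here is random, so nothing that happens afterwards can be one. Sessions completed and on-study dose may instead be consequences of assignment. Conditioning on them can remove part of the treatment effect, or introduce bias through causes they share with the outcome.

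Dose matters most for interpretation. Section 5 (Summary of Study Design) asks whether medication falls while NBSS stays stable. A model that holds on-study dose fixed asks how NBSS compares between arms at the same dose, which is another question. NBSS and the voiding diary make up Primary Objective 2, so the affected results are not peripheral. If the adjusted model and the unadjusted test disagree, the plan has no rule for which one counts. Because the dose covariate is undated, its meaning could also be chosen after the data are seen.

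**Working it through.** **1. The plan's own figure.** The covariate list has no figure attached. The nearest is the Aim 1.1 sample size in Section 11.1: 83% v 40%, 80% power, two-sided 0.05, 21 per group. With pooled variance and mean proportion 0.615:

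n = [1.96 × √(2 × 0.615 × 0.385) + 0.842 × √(0.83 × 0.17 + 0.40 × 0.60)]² / 0.43² ≈ 18.9, so 19 per group.

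This is close to 21, and power at 21 is 84.3%. The calculation is an unadjusted comparison of proportions, so the covariate problem does not touch it.

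**2. Timing of each covariate.**

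| Covariate | Fixed before randomisation? |
|---|---|
| Age, sex, severity of SCI | Yes |
| Number of sessions | No; accrues over the 3 months |
| OAB dose, if baseline | Yes |
| OAB dose, if on-study | No; weaned from week 3 by tolerance |

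**3. Sessions.** In SD units, the arm coefficient shifts in absolute size by

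(arm difference in sessions) × (within-arm correlation of sessions with outcome).

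Both inputs are assumed. The simulation used 8,000 replicates, 30 per arm and no true effect.

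| Difference in sessions | Correlation | Formula | Simulated shift | Rejection at nominal 0.05 |
|---|---|---|---|---|
| 0 | 0.2 / 0.4 | 0 / 0 | 0.00 / 0.00 | 0.049 / 0.051 |
| 0.25 SD | 0.2 / 0.4 | 0.05 / 0.10 | 0.048 / 0.102 | 0.058 / 0.071 |
| 0.5 SD | 0.2 / 0.4 | 0.10 / 0.20 | 0.105 / 0.199 | 0.072 / 0.127 |

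**4. On-study dose.** A large simulation (N = 2,000,000) took 83% v 40% reducing medication from Section 11.1. Everything else is assumed: NBSS intraclass correlation 0.6, no direct arm effect, and a correlation between tolerance of weaning and NBSS of 0.09, 0.25 or 0.49. Entries are the adjusted minus the total arm effect on week-12 NBSS in SD, in that order of correlation. A positive value makes TTNS look worse than it is.

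| Use of baseline NBSS | Tolerance depends on | Reduction has no effect on NBSS | Reduction worsens NBSS by 0.4 SD |
|---|---|---|---|
| Covariate | Stable severity | +0.03 / +0.08 / +0.16 | -0.15 / -0.10 / -0.01 |
| Covariate | Current symptoms | +0.04 / +0.12 / +0.24 | -0.13 / -0.06 / +0.07 |
| Change score | Stable severity | 0 / 0 / 0 | -0.17 / -0.17 / -0.17 |
| Change score | Current symptoms | +0.03 / +0.07 / +0.14 | -0.15 / -0.10 / -0.03 |

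The value -0.17 can be checked by hand. The arms differ by 0.83 - 0.40 = 0.43 in the proportion reducing, and 0.43 × 0.4 = 0.172. That is the part of the effect that runs through dose, and the adjustment removes it.

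**5. Baseline dose.** A second simulation (400,000 subjects, all coefficients assumed) set a direct arm effect of -6, a dose 0.43 units lower on TTNS, and a 3-point fall in score per unit of dose. The total effect is -6 + 0.43 × 3 = -4.71. The unadjusted model gave -4.70, the model with baseline dose -4.70, and the model with on-study dose -5.99. Adjusting for baseline dose leaves the total effect intact; adjusting for on-study dose does not.

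**The case against.** The case on the other side is substantial.

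- **Sessions may not differ by arm.** Both arms get the same instruction, the sham is meant to be convincing, and the stipends and weekly calls are described without distinction by arm. No section predicts a difference. This stands, and without a difference there is no bias. It does not rule one out. The stimulation differs (just under motor threshold v 1 mA), and the listed reasons for discontinuing include intolerance of stimulation and intolerable incontinence, so session counts can reflect outcome. The full compliance in Pilot Trial I came from 10 days with hospital staff, not 3 months at home.
- **Baseline dose is the more natural reading.** On-study dose could not adjust a model of itself, whereas baseline dose could serve every outcome. This is a fair argument, but the text does not settle it, and a longitudinal model with monthly medication logs leaves the other reading open.
- **The unadjusted tests remain.** They do, for the Aim 1 and Aim 2 outcomes. I-QOL and the anticholinergic survey are collected only at baseline and 3 months, so the problem mainly concerns NBSS and the diary.
- **The illustrations are not the planned model.** They use one end-point and a yes/no reduction, not repeated measures with actual doses, and the session runs ignore dropout. The -0.17 SD is also a change of question more than a bias. Both points stand; the figures show only what is possible.
- **The dose point may shrink.** Section 1 (Rationale for Study Design) describes discontinuation after 2 weeks, while Section 5 describes gradual weaning. If everyone discontinued, on-study dose would differ little by arm. The two passages must be reconciled.

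**Conclusion.** The concern holds. Naming sessions as a confounder is wrong on any reading. The dose covariate is harmless on one reading and, on the other, conditions on the outcome of Primary Objective 1. The claim is only that the mixed-model arm coefficient need not estimate the total randomised effect. The documents do not determine the size or direction of a shift.

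Under the stated assumptions the illustrative range is -0.17 to +0.24 SD for on-study dose, including 0. For sessions it is 0 to 0.20 SD, for arm differences of up to 0.5 SD and correlations of up to 0.4. The Aim 1.1 sample size and the unadjusted comparisons are untouched, and the covariates of the Bayesian analysis are not stated. This should be fixed before analysis, but it does not undermine the design.

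**What to change.** In Section 11.2:

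1. Restrict the efficacy mixed models to pre-randomisation covariates: complete/incomplete SCI (the stratification factor), the baseline value of the outcome, age, sex, and OAB dose written explicitly as dose at baseline. A model that treats the baseline outcome as one of the repeated responses would also do.
2. Move any model containing number of sessions or on-study dose to a labelled exploratory analysis that is not reported as the treatment effect.
3. State for each outcome whether the mixed model or the unadjusted test is primary. This is a related gap; items 1 and 2 are worth making without it.

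The cost is SAP wording only. The data are already collected, and neither the sample size, the visits nor the clinical procedures change.
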